10.6.2. Serious adverse events (SAE) and serious adverse drug reactions (SADR)

A serious adverse event or serious adverse drug reaction is any untoward medical occurrence that at any dose

- results in death

- is life-threatening at the time of the event
- requires inpatient hospitalization or prolongation of existing hospitalization
- results in persistent or significant disability/incapacity
- is a congenital anomaly or birth defect
- is medically important condition

Inpatient hospitalization is defined as any stay in hospital on the part of a patient that includes at least one night (midnight to 06:00). Scheduled admission to hospital before first admission of IMP are not SAEs, but must be documented in the proper manner in patient's medical records and CRF.

10.6.3. Unexpected adverse drug reaction (UADR)

An unexpected ADR is an ADR whose nature or severity is not consistent with the applicable product information available for the IMP. Expected ADRs are listed in the Summary of Product Characteristics (SmPC, Information Sheet for Health Professionals [Fachinformation in Germany]).

10.6.4. Suspected unexpected serious adverse reactions (SUSAR)

A suspected unexpected serious adverse reaction (SUSAR) is an AE whose nature or severity is not consistent with the product information available for the IMP, is regarded as serious, and has at least a possible causal relationship with the IMP.

10.6.5. Causal relationship between adverse event and IMP

The causality will be initially assessed by the investigator. For causality assessment, a binary grading will be used:

- Related/ "Reasonable Possibility": Any AE for which there is a reasonable possibility that the drug caused the AE. A *reasonable possibility* means there are facts (evidences) or arguments to suggest a causal relationship, regardless of whether there are less or more degrees of certainty between the drug and the AE.
- Not Related/ "No Reasonable Possibility": Any AE for which there is not a reasonable possibility that the drug caused the AE.

10.6.6. Documentation and follow-up of adverse events

Documentation of AEs will begin with study start (date of treatment visit). All AEs will be documented in the CRF including following information:

- AE description
- Severity
- Causal relationship with IMP / study treatment
- Expectancy
- Seriousness

- Action taken
- Outcome
- Date of onset and resolution

Regardless of whether a causal relationship between the AE and the IMP is suspected, patients who develop AEs must be monitored until all symptoms have subsided, pathological laboratory values have returned to pre-event levels, a plausible explanation is found for the AE, the patient has died or the study was terminated for the patient concerned.

All AEs and SAEs, including those that are ongoing at date of study termination, will be followed up until resolution or until the investigator decides that no further follow-up is necessary. Anyhow, ongoing AEs will be followed up within a period of 28 days after study termination at the latest.

Treatment of AEs is at the discretion of the investigator and should follow the standards of medical care at the investigator's institution.

10.6.7. Reporting of serious adverse events and pregnancy

The investigator and other center personnel must inform the appropriate Mitsubishi Tanabe representatives of any SAE and pregnancy that occurs during the study within 24 hours of being made aware of such. Follow-up information on SAEs must also be reported by the investigator within the same time frame.

All correspondence on pharmacovigilance and information on SAEs as well as pregnancies should be addressed to:

Mitsubishi Tanabe Pharma Europe Ltd.
Safety Department
[name]
[name]
[name]
United Kingdom

[REDACTED]

10.6.8. Assessment of event by sponsor

All cases of suspected SAEs are assessed by the sponsor and the investigator with regard to seriousness, causality and expectedness.

10.6.9. Notification of ethics committee and competent supreme federal authority

Every SUSAR that becomes known in a clinical trial will be reported by the sponsor or investigator to the competent supreme federal authority and the ethics committee.

Fatal and life-threatening SUSARs

The competent supreme federal authority and the responsible ethics committee must be informed of all fatal or life-threatening SUSARs by the sponsor or investigator. This must be done without delay, at the latest 7 calendar days after becoming aware of the minimum criteria for reporting. In all cases, attempts must be made to obtain further relevant information which must be supplied to the

competent supreme federal authority and the ethics committee within a time-span of another 8 days. Furthermore, if a patient dies, this information must be passed on to the ethics committee responsible for the region in which the death occurred.

SUSARs that are not fatal or life-threatening

The competent supreme federal authority and the ethics committee responsible will be informed without delay by the sponsor or investigator of all SUSARs, at the latest within 15 calendar days of becoming aware of the minimum criteria for reporting. Further relevant details will be passed on as soon as possible.

If the information at the time of reporting is incomplete, further information to enable adequate assessment of the case will be requested from the reporter or other available sources.

10.6.10. Review and reporting of changes in the risk-benefit ratio

Without delay, and at the latest within 15 days of the decision for the need to do so, the sponsor or investigator will inform the competent supreme federal authority and the ethics committee responsible of any events or factors that mean that the risk-benefit ratio of the IMP has to be reviewed. Especially:

- Individual reports of expected serious ADRs with an unexpected outcome
- A clinically relevant increase in the rate of occurrence of expected SADRs
- Factors emerging in connection with trial conduct or the development of the IMP that may affect the safety of persons concerned.

10.6.11. Informing the investigators

The investigator will also inform his substitute of all SAEs.

11. Quality management

11.1. Risk management

In order to secure the quality of study conduct and study data, respective quality assurance measures are implemented.

Quality of Study Conduct

The conduct of the study is aiming to treat study patients at the highest possible level of safety and efficacy. SAICoDis specifically addresses the question whether the infusion of Argatroban may be associated with the risk of prolongation of the QTc interval. Therefore, internal data monitoring will be performed by reviewing the results of ECG evaluation. Each study center nominates an ECG expert if specific advices are required.

Antithrombotic Prophylaxis

Since the invasive PCI procedure, particularly in combination with stent implantation is associated with increased procoagulant risk, patients undergoing PCI receive both antiplatelet and anticoagulant therapy. The antiplatelet agent(s) are given pre- and post-interventionally, while the

anticoagulant drug is usually applied only during the intervention. Argatroban shows a shorter half-life time compared to standard anticoagulant unfractionated heparin. This difference of pharmacokinetics has been addressed by adjusting the study protocol in such a way that intervention procedure is only to be initiated, when either antiplatelet therapy has reached already a steady-state level, or a bolus of the antiplatelet drug is administered before start of PCI.

This aspect is subject of continuous training of study physicians.

Consistency ECG and laboratory data

Collected ECG data and Argatroban plasma levels, each of which are assessed at one single site in order to secure highest level of consistency.

The ECG records are pseudonymized so that the ECG evaluator is blinded for patient-ID and time of ECG recording. A patient identifier is assigned to each ECG by CRO to assemble the 3 ECG sets of each patient in relationship to time of recording.

Personal Data Protection

The DSGVO and the respective Data Protection Policy of the sponsor apply to all patient data at all times. All staff of study centers, CRO, and sponsor involved in SAICoDis project are obliged to observe the DSGVO. The privacy of all collected patient data is secured by omitting any information on CRFs which may allow an identification of the individual. The data set related to a screened / treated study patient are characterized by a specific patient number assigned exclusively to an individual patient.

11.2. Data quality assurance

11.2.1. Monitoring

All trial site will be monitored to ensure the quality of the data collected. Monitoring will be made for study initiation, during the study and for study closure to ensure that all aspects of the protocol are followed. The objectives of the monitoring procedures are to ensure that patient's safety and rights as a study participant are respected, that accurate, valid and complete data are collected, and that the trial is conducted in accordance with the trial protocol, the principles of GCP and local legislation.

The investigator agrees that a monitor regularly visits the trial site and assures that this monitor will receive appropriate support in activities at the trial site. The declaration of informed consent (see Section 14.4) includes a statement to the effect that the monitor has the right – while observing the provisions of data protection legislation – to compare CRFs with patient's medical records (doctor's notes, ECGs, laboratory printouts etc.). The investigator must allow the monitor access to all necessary documentation for trial-related monitoring. Aims of these monitoring visits are as follows:

- To check the declarations of informed consent
- To monitor patient safety (occurrence and documentation/reporting of AEs and SAEs)
- To check the completeness and accuracy of entries on the CRFs
- To validate entries on the CRFs with source documents (source data verification, SDV),
- To perform drug accountability checks
- To evaluate the progress of the trial

- To evaluate compliance with the trial protocol
- To assess whether the trial is being performed according to GCP at the trial site
- To discuss with the investigator aspects of trial conduct and any deficiencies found

A monitoring visit report is prepared for each visit describing the progress of the clinical trial and any problems.

11.2.2. Audits

Authorized representatives of the sponsor or a regulatory authority may visit the trial site to perform audits or inspections, including source data verification. The aim of an audit is to verify validity, accuracy and completeness of data, to establish credibility of the clinical trial, and to check whether the patient's rights and safety are being maintained. The purpose of a Mitsubishi Tanabe audit is to determine that data were recorded, analysed and accurately reported according to the protocol, the principles of GCP, the ICH guidelines and any applicable regulatory requirements. The sponsor may assign these activities to persons otherwise not involved in the trial (auditors). These persons are allowed access to all trial documentation (especially the trial protocol, CRFs, patients' medical records, drug accountability documentation, and trial-related correspondence).

Sponsor and trial site agree to support auditors and inspections by competent authorities at all times and to allow persons charged with these duties access to the necessary original documentation.

All persons conducting audits pledge to keep all patient data and other trial data confidential.

12. Data Management

Data management will be performed according to the determinations within the data management plan. The data management plan will describe in greater detail the methods used to collect, check and process clinical data. It will include a description of the plausibility and consistency tests that must be run during data processing as well as rules defining how to deal with any discrepancies.

For computerized data entry and data analyses standardized procedures will be used. All data will be entered double and independently by different persons in a validated study data base and checked for discrepancies.

Before data can be entered in the study data base all data are checked for correctness, plausibility and completeness. Additionally, these checks will be performed during and after data entry in the data base.

The data manager will contact the respective study center in writing, in order to resolve any occurring discrepancy. Investigators should answer queries in a timely manner.

Statistical analysis will be performed only after the study data base has been closed and declared as „Clean File“.

12.1. Study documentation, CRFs and record keeping

12.1.1. Investigator's file / retention of documents

Investigators must maintain adequate and accurate records to enable the conduct of the study to be fully documented and the study data to be subsequently verified. These documents should be classified into two different separate categories: Investigator's study file and patient data.

The investigator's study file will contain all essential documents: the protocol/amendments, CRF and query forms, patient information and informed consent form, ethics committee and federal regulatory authority approval, notification of the federal regulatory authority and competent regional authorities, drug records, staff curriculum vitae and authorization forms and other appropriate documents/correspondence etc.

Patient data include patient hospital/clinic records (medical reports, OP reports appointment book, medical records, pathology and laboratory reports, ECG, EEG, X-ray, etc.), signed informed consent forms, patient screening and identification forms.

The investigator must keep these two categories of documents on file for at least 15 years (or more as legally required) after completion or discontinuation of the study. The documents must be archived in a secure place and treated as confidential material. Should the investigator wish to assign the study records to another party or move them to another location, the sponsor must be notified in advance.

12.1.2. Source documents and background data

On request, the investigator shall supply the sponsor with any required background data from the study documentation or clinic records. This is particularly important when CRF entries are illegible or when errors in data transcription are suspected. In case of special problems and/or governmental queries or requests for audit inspections, it is also necessary to have access to the complete study records, providing that patient confidentiality is protected. According to the standards of the data protection law, all data obtained in the course of a clinical study must be treated with discretion in order to guarantee the rights of the patient's privacy.

12.1.3. Case report form

For each patient enrolled, the CRF must be completed and signed by the principal investigator or authorized delegate from the site staff. These signatures serve to attest that the information contained within the CRFs is complete and true. At all times, the principal investigator has final personal responsibility for the accuracy and authenticity of all clinical and laboratory data entered on the CRFs. Patient source documents are the physician's patient records maintained at the site. In most cases, the source documents will be the hospital's or the physician's chart. In cases where the source documents are the hospital's or the physician's chart, the information collected on the CRFs must match those charts. Corrections shall be signed and dated and the originally entered data shall stay visible.

12.1.4. Audits and inspections

This study may be audited by the sponsor, any person authorized by the sponsor or the competent health authority in order to determine the authenticity of the recorded data and compliance with the

study protocol. The investigator should understand that source documents for this trial should be made available to qualified personnel from sponsor/monitors/auditor/health authority inspectors after appropriate notification. These documents are needed for source data verification and proper review of the study progress. CRF data must be verified by direct inspection of source documents. The investigator agrees to comply with sponsors and regulatory authority requirements regarding auditing of the study. All material used in clinical studies are subjected to quality control.

13. Sample size calculation and statistical methods

13.1. Sample size calculation

A one-sided one sample t-test with a significance level of 5% will be used to test the primary hypothesis of this study that QTc will not increase more than 10 ms under argatroban. Table 1 depicts the power of the test with 45 evaluable patients for varying population means Δ QTc.

Δ QTc in population	Power	β
0	> 0.999	< 0.001
1	> 0.999	< 0.001
2	> 0.999	< 0.001
3	0.999	0.001
4	0.990	0.010
5	0.951	0.049
6	0.841	0.159
7	0.632	0.368
8	0.373	0.627

Table 1: Power of test (one-sided one sample t-test, alpha=5%, n=45 evaluable patients)

Up to a population mean of Δ QTc = 6 the power of the test will be adequate, i.e. > 0.8 . To account for potential dropouts at least 50 patients will be enrolled into the study, assuming a dropout rate of about 10%.

13.2. Randomisation

Not applicable.

13.3. Statistical methods

13.3.1. Study population definitions

Each patient will be assigned to appropriate analysis populations for statistical analysis. The different analysis populations are:

- All enrolled population

All patients enrolled into the study regardless if they were treated or not.

- Intention to treat population (ITT population), safety population:

All patients who took at least one dose of treatment.

- Per protocol population (PP population):

All patients in the ITT population fulfilling the criteria for inclusion, none of the exclusion criteria and also complied to study design.

13.3.2. Disposition

Description of patients' disposition will be based on the all enrolled population. The number of patients enrolled and treated or not treated, will be depicted total and by center. A listing will be provided of all patients who discontinued treatment or study, including the reason for withdrawal.

This section will give details about the number of patients adhering to the inclusion criteria of the protocol and the number of patients fulfilling exclusion criteria. A listing will be provided of all patients who were excluded from each analysis population.

13.3.3. Demographic characteristics

Patients' continuous demographic and baseline variables will be summarized using descriptive statistics (mean, standard deviation, median, minimum and maximum), while categorical variables will be summarized using frequency tabulations. Individual patient listings will be provided.

13.3.4. Study drug

For argatroban dosage, statistics (mean, standard deviation median, minimum and maximum) will be provided for the dose level achieved during bolus, prolonged argatroban infusion and the cumulative dose. Duration of exposure will be similarly outlined with a summary of dosing interruptions and reductions.

13.3.5. Safety evaluation

Description of safety will be based on the ITT population. The primary variable will also be analysed by the PP population.

13.3.5.1. QTc - Statistical hypothesis (primary variable)

Following measurements of QTc will be made for each patient:

- Prior to first bolus dose of argatroban: QTc₁
- immediately after cardiac intervention in a status of full anticoagulation with argatroban: QTc₂
- > 8 but ≤ 28 hours after termination of prolonged argatroban infusion: QTc₃

The statistical hypothesis of this study refers to the difference QTc₂ minus QTc₁ = Δ QTc:

H₀: Δ QTc > 10 ms

H_A: Δ QTc ≤ 10 ms.

H_0 will be tested by a one-sided one sample t-test with a significance level of alpha=5%. Data from all patients with measurements QTc₁ and QTc₂ will be included in the analysis of Δ QTc.

Additionally, Δ QTc as well as QTc₁ and QTc₂ will be described by descriptive statistics (mean, standard deviation, median, minimum, maximum, and 95%-confidence interval). An individual patient listing will be provided with QTc₁, QTc₂, Δ QTc, QTc₃ and the difference QTc₃ minus QTc₁.

The analysis of the primary variable will be based on the ITT sample. It will be repeated for the PP sample. The study report will contain a statement about difference in study results between the ITT and PP sample.

13.3.5.2. Secondary target variables

- Mean difference in QTc interval between ECG-3 and ECG-1.

The difference QTc₃ minus QTc₁ will be defined by descriptive statistics. If the 95%-confidence interval includes the value 0, a return of QTc-values to baseline values will be stated.

- Proportion of patients with a prolongation of QTc interval to > 500 ms at ECG-2.
- Proportion of patients with a prolongation of QTc interval to > 500 ms at ECG-3.
- Proportion of patients with a prolongation of QTc interval of > 60 ms at ECG-2 compared to ECG-1.
- Proportion of patients with a prolongation of QTc interval of > 60 ms at ECG-3 compared to ECG-1.

One-sided 95%-Pearson-Clopper confidence limits will be computed for those proportions.

- Incidence of haemorrhagic events according to the definition of CABG-related bleeding.

A two-sided 95%-Pearson-Clopper confidence limit will be computed for the proportion of patients with haemorrhagic events.

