	
H_0 will be tested by a one-sided one sample t-test with a significance level of alpha = 5%. Data from all patients with measurements QTc₁ and QTc₂ will be included in the analysis of Δ QTc.
 
Additionally, Δ QTc as well as QTc₁ and QTc₂ will be described by descriptive statistics (mean, standard deviation, median, minimum, maximum, and 95%-confidence interval). An individual subject listing will be provided with QTc₁, QTc₂, Δ QTc, QTc₃ and the difference QTc₃ minus QTc₁.
 
The analysis of the primary variable will be based on the ITT sample. It will be repeated for the PP sample. The study report will contain a statement about difference in study results between the ITT and PP sample.
 
 • Mean difference in QTc interval between measurements at ECG-3 and ECG-1. 
The difference QTc₃ minus QTc₁ will be described by descriptive statistics. If the 95%-confidence interval will include the value 0, it will be said that QTc-values returned to their baseline values.
 
 • Proportion of patients with a prolongation of QTc interval to > 500 ms at ECG-2. • Proportion of patients with a prolongation of QTc interval to > 500 ms at ECG-3. • Proportion of patients with a prolongation of QTc interval of > 60 ms at ECG-2 compared to ECG-1. • Proportion of patients with a prolongation of QTc interval of > 60 ms at ECG-3 compared to ECG-1. 
One-sided 95%-Pearson-Clopper confidence limits will be computed for those proportions.
 
 • Incidence of haemorrhagic events according to the definition of CABG-related bleeding. 
A two-sided 95%-Pearson-Clopper confidence limit will be computed for the proportion of patients with haemorrhagic events.

GCP conformance	The present trial protocol and any amendments were and will be prepared in accordance with the Declaration of Helsinki adopted by the 18 th World Medical Assembly, Helsinki, Finland, 1964 and later revision (October 2013, 64 th General Assembly of the World Medical Association, Fortaleza, Brazil).

	
The present clinical trial will be conducted in accordance with the published principles of the guidelines for Good Clinical Practice (ICH-GCP) and applicable legislation (especially the Federal Drug Law [AMG] and the GCP-V).

Financing	
The clinical trial will be financed by Mitsubishi Tanabe Pharma GmbH [name] [name]

3. Flow chart

[figure not shown]

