In general, 3 to 24 hours prior to intervention a clopidogrel loading dose of 600 mg will be administered. In addition to clopidogrel the patient receives a loading with 250 mg ASA (orally or i.v.). The early dual platelet inhibition therapy is applied due the rapid offset of the anticoagulation effect upon termination of argatroban infusion at the end of the PCI. The offset of argatroban effect has been observed within 30 minutes after stop of the infusion. Thus, a potential gap of sufficient antithrombotic protection may be obtained if the dual antiplatelet therapy is only started after termination of argatroban infusion. The ARG-E04 study [5] revealed an effective and safe persistent antithrombotic protection if dual antiplatelet therapy was instituted before PCI commenced.

After getting an argatroban bolus dose of 300 µg/kg (administered over 3 to 5 min), the patient receives an argatroban maintenance dose infusion of 20 µg/kg/min. The argatroban infusion will be stopped at the end of the PCI (removal of the guiding catheter or the sheath).

To monitor reliability of anticoagulation, ACT will be measured as a routine parameter of anticoagulation for PCI. In general, ACT measurements will be started and performed with the placement of the vascular sheath (starting the intervention). Therefore, plasma samples will be obtained 5 minutes after completion of injection of the bolus dose and at 5 min after completion of every further bolus or treatment adjustment. Depending on clinical relevancy further ACT assessments are possible.

If target ACT is reached, the intervention can be continued.

If ACT remains below the target of 300 s, patients will receive an additional i.v. bolus injection of 150 µg/kg and the infusion dose will be raised up to 30 µg/kg/min. In case ACT > 450 s, the infusion dose will be reduced to 15 µg/kg/min. As soon as the target ACT (between 300 s and 450 s) is reached infusion dose shall remain unchanged during PCI procedure. If clinically necessary, the hematocrit value will be measured during the treatment.

The PCI will be conducted according to usual clinical routine of the investigator site. The PCI starts with the placement of the vascular sheath and ends with re-movement of this sheath. Immediately after PCI, a study-specific 12-lead ECG (ECG-2) will be recorded in the catheter lab at a time of steady state anticoagulation with argatroban.

Follow-up phase (ends > 8 but ≤ 28h after PCI):

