14.4 Exploratory analyses

If p-values are calculated for secondary endpoints they need to be interpreted descriptively and non-confirmatory only.

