15.5 Efficacy evaluation

The primary data set for the efficacy analysis will be the ITT analysis set. Additional analyses will be performed for the PP analysis set. Note that whereas trials to show superiority always use the ITT population as primary analysis, results for both ITT and PP population are of interest in non-inferiority trials. It may actually be easier to show non-inferiority in the bigger sample of the ITT population, especially in case of many protocol deviations. This underpins the importance of the PP analysis in non-inferiority trials.

Subgroup analyses will be performed as described in Section 14.6.

Summary tables will be provided by means of descriptive statistics and frequency tables, as appropriate.

15.5.1 12-lead ECG

The following will be presented at screening, during treatment and at follow-up:

- Overall interpretation (investigator and blinded ECG-reader assessment); if abnormal, clinically significant
- Measured QT interval, corrected QT interval
- Interpretation of QT interval: prolonged; if prolonged, clinically significant

Primary endpoint (see section 12.1):

- Difference in QTc interval between ECG-2 and ECG-1 ($\Delta QTc = QTc_2 - QTc_1$)
- Test of statistical hypothesis (see Section 14.3)

Secondary endpoints (see section 12.2):

- Difference in QTc interval between ECG-3 and ECG-1 ($QTc_3 - QTc_1$)

- Proportion of patients with $QTc_2 > 500$ ms
- Proportion of patients with $QTc_3 > 500$ ms
- Proportion of patients with $QTc_2 - QTc_1 > 60$ ms
- Proportion of patients with $QTc_3 - QTc_1 > 60$ ms

In addition, a listing will tabulate the individual response data, i.e. QTc_1 , QTc_2 , QTc_3 as well as gender and cumulative Argatroban dose.

The dependence of QTc interval on gender and cumulative Argatroban dose will furthermore be investigated in plots. If applicable, linear correlation of QTc interval and cumulative Argatroban dose will be assessed.

Heart rate and Measured RR interval will be presented at screening, during treatment and at follow-up.

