15.6.2 Individual patient data listing of adverse events

All adverse events, treatment emergent or not, will be listed in an individual patient data listing. Verbatim adverse event terms will be depicted along with the assigned

MedDRA preferred term, treatment, intensity, seriousness, relation, measures regarding study treatment and patient, start of AE, end of AE, and visit dates.

A separate listing will be provided for deaths, other serious adverse events, and other significant adverse events.

16 Statistical software used for analysis

Statistical analysis will be conducted using the program system SAS (Version 9.4 or later) under the Microsoft Windows 10 Professional operating system (or later) at the computer facilities of [REDACTED].

17 Reporting of analyses

Percentage values will be printed with two digits to the right of the decimal point. All p-values will be given by four digits to the right of the decimal point.

Verbatim terms documented on the CRF will be presented as entered.

The statistical analysis output will be prepared in English. The separate individual patient data listings will be in original CRF language. The separate individual patient data listing will include patients excluded from the ITT analysis set, if any.

18 Changes to planned analyses

This statistical analysis plan does currently not include any relevant changes to the planned analyses that are described in the study protocol.

[figure not shown]
Any changes made to the SAP after sign-off must be signed-off as a SAP Amendment, detailing the old text, revised text and reason for change.

19 Graphics, analysis tables and listings

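### The rule that declares QTc back to baseline whenever the 95% CI for QTc3 minus QTc1 includes 0 treats failure to find a difference as proof that there is none

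*Protocol*

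**What the plan says.** Protocol section 13.3.5.2 treats the mean of QTc3 minus QTc1 descriptively and then attaches a conclusion to it: "If the 95%-confidence interval includes the value 0, a return of QTc-values to baseline values will be stated". The synopsis, under statistical methods, has the same rule: "If the 95%-confidence interval will include the value 0, it will be said that QTc-values returned to their baseline values". Neither place gives a margin, a limit on the width of the interval or a power statement, and neither says what will be reported if the interval excludes 0.

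The SAP neither repeats nor cancels the rule:

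- Section 15.5.1 only lists the endpoint ("Difference in QTc interval between ECG-3 and ECG-1").
- Section 14.4 restricts p-values but not statements based on an interval: "If p-values are calculated for secondary endpoints they need to be interpreted descriptively and non-confirmatory only".
- Section 18 says: "This statistical analysis plan does currently not include any relevant changes to the planned analyses that are described in the study protocol".

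The protocol sentence therefore still governs the report.

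**The concern.** For a mean difference, a two-sided 95% t interval includes 0 exactly when the two-sided 5% t-test is not significant. The rule therefore turns a failure to reject *no difference* into a positive finding of *no difference*.

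It also rewards imprecision. If some residual shift exists, more noise or more missing ECG-3 recordings raise the chance of the reassuring statement, and a small, precisely estimated shift blocks it. SAP section 14.1.2 uses observed cases only, so every lost ECG-3 recording widens the interval.

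The primary analysis in the same protocol uses the right logic: to conclude that QTc does not rise by more than 10 ms, it must reject a null hypothesis of a larger rise. At stake is whether the report states reversibility of QTc when the data may not support it, in a trial whose subject is QTc and whose first secondary objective is QTc after wash-out.

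**Working it through.** **Inputs.** Evaluable n = 45, with 50 enrolled and about 10% dropout (protocol 13.1). The SD of QTc3 minus QTc1 is not stated. The interval is taken as two-sided for the mean; the protocol does not give its sidedness.

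**Step 1: the SD implied by the plan.** Table 1 in protocol 13.1 ("Power of test (one-sided one sample t-test, alpha=5%, n=45 evaluable patients") gives power but no SD. Power is P(T < t(0.05, 44)), where T is non-central t with 44 df and non-centrality (μ − 10)·√45/SD. Solving for the SD in the rows for 4 to 8 ms gives 9.98, 10.01, 9.99, 10.00 and 10.00 ms. With SD = 10 the table is reproduced:

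| True mean (ms) | 4 | 5 | 6 | 7 | 8 |
|---|---|---|---|---|---|
| Stated power | 0.990 | 0.951 | 0.841 | 0.632 | 0.373 |
| Recomputed | 0.990 | 0.951 | 0.841 | 0.632 | 0.373 |

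This SD belongs to QTc2 minus QTc1. Using it for ECG-3 is an assumption, so SDs of 15 and 20 ms are shown as well. The documents do not supply those two values.

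**Step 2: which observed results earn the statement.** The half-width is t(0.975, 44)·SD/√45 with t = 2.015. It is 3.00 ms at SD 10, 4.51 ms at SD 15 and 6.01 ms at SD 20.

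- Mean +3.1 ms, SD 10: CI 0.1 to 6.1 ms, so no statement.
- Mean +4.4 ms, SD 15: CI −0.1 to 8.9 ms, so QTc is said to have returned.

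The larger and less certain shift gets the reassurance.

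**Step 3: how often a true residual is called returned.** P(CI includes 0) = P(|T| < t(0.975, n−1)), where T is non-central t with n−1 df and non-centrality shift·√n/SD. At n = 45:

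| SD (ms) | +3 ms | +5 ms | +8 ms |
|---|---|---|---|
| 10 (implied for QTc2 − QTc1) | 50% | 9% | <0.1% |
| 15 (assumed) | 74% | 41% | 6% |
| 20 (assumed) | 83% | 63% | 25% |

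**Step 4: effect of losing ECG-3 recordings.** With a true +5 ms and SD 10, the chance of the statement is 7% at n = 50, 9% at n = 45, 13% at n = 40 and 25% at n = 30.

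**Step 5: can a *returned* interval still contain 10 ms?** This uses the primary limit only as a yardstick. The interval must span 0 to 10 ms, so 2·t(0.975, n−1)·SD/√n must be at least 10. At n = 45 that needs an observed SD above 10·√45/(2 × 2.015) = 16.6 ms. At SD 10 the largest observed mean that earns the statement is +3.0 ms, with an upper limit of 6.0 ms. By simulation with a true +5 ms and n = 45, the statement and an upper limit of at least 10 ms occur together less than 0.01% of the time at SD 10, about 1% at SD 15 and about 25% at SD 20.

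**The case against.** The case for leaving the rule, or calling it minor, is as follows. On the only SD the plan implies and the planned n, false reassurance is mostly confined to mean residuals of about 2 to 4 ms, well below the 10 ms that the trial uses for its primary question. The larger probabilities need SDs that the documents do not support. The endpoint is secondary and descriptive. The safety alerts and the stopping example (protocol 8.6 and 9.3) use individual values above 500 ms or increases above 60 ms, not the ECG-3 mean.

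Wash-out also makes a return plausible. On anticoagulation, protocol 6.3 says: "The offset of argatroban effect has been observed within 30 minutes after stop of the infusion". ECG-3 comes more than 8 hours after the infusion and should be postponed, up to 28 hours, while ACT is above 160 s. Readers will also have individual QTc3 minus QTc1 values, the ECG-3 proportions, and a listing of argatroban concentration, dTT and ACT beside the ECG-3 QT interval (SAP 15.4).

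Much of this stands, and it limits the weight of the point. The size of the problem for ECG-3 is unknown, not shown to be large. But the offset and ACT arguments concern anticoagulation and do not make the inference about mean QTc valid. The listings let a careful reader check the wording, yet the report would still have to carry a sentence its interval may not support. The word *descriptive* does not help when the conclusion is mandatory.

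**Conclusion.** The concern holds. The rule is wrong as written: it states return to baseline on the strength of a non-significant difference, and nothing in the SAP removes it. The logical error does not depend on any assumed figure.

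Its practical size does. If the SD of QTc3 minus QTc1 is near 10 ms and about 45 ECG-3 recordings are available, a mean residual of 8 ms or more would almost never be missed, while one of 3 ms would be missed about half the time. A larger SD or fewer recordings makes it worse. The damage is limited to one secondary conclusion; the primary test and the sample size are not touched. It should be fixed because the correction costs almost nothing.

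**What to change.** **Preferred route, in the SAP.** Add to section 15.5.1: *The mean of QTc3 minus QTc1 will be reported with its two-sided 95% confidence interval, and the report will state the largest prolongation this interval does not exclude. The return-to-baseline sentence in protocol section 13.3.5.2 and the synopsis is not applied.* Record this in SAP section 18 before database lock. If the SAP is already signed, its own rule applies: "Any changes made to the SAP after sign-off must be signed-off as a SAP Amendment".

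**Protocol route.** Replace the sentence in section 13.3.5.2 and in the synopsis, and add the same line to SAP 15.5.1. Protocol section 16 requires agreement of the named parties, written reasons and the signatures of all original authors, plus submission if the change needs approval. The planned last visit was Q1 2021 and the SAP cites a data management plan of 15 April 2021. On planned dates a protocol amendment would follow the last visit, so the SAP route is the simpler one.

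**If a statement of return is wanted.** Make it only when the two-sided 95% CI lies wholly within a prespecified, justified two-sided margin. If only an upper limit is used, word it as *no residual prolongation above X ms*. The sponsor must justify the margin for ECG-3 and not carry over the on-drug 10 ms by default. At n = 45 and SD 10, a margin of ±10 ms would call a true +5 ms returned 91% of the time and +8 ms 26%. A margin of ±5 ms would do so 2.5% of the time at +5 ms and 81% at a true 0.

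**Cost.** One line and one entry in the SAP. No extra data are needed, and the sample size and primary test do not change.
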